Patient reward programs may help to overcome present bias by providing patients with a timely, tangible reward for achieving a health-related goal. There is a growing body of evidence suggesting that rewards work for some health behaviors, including smoking, medication adherence, vaccinations and screening. Rewards are especially effective among lower-income patients, who are common in the VA population. There has been robust success using rewards for treatment of substance abuse, where it is referred to as contingency management (CM). CM has been widely implemented in addiction treatment clinics across the VA.

Financial rewards for weight loss are also effective. Several meta analyses and systematic reviews have studied the variety of forms of financial rewards, designed to make use of common decision errors. Group-based payments allow individuals who achieve a weight loss goal to share the reward of individuals in their group who failed to meet the goal, which takes advantage of our tendency to assume that we are each better than average. Lotteries take advantage of our tendency to over-estimate the probability of rare events. Deposit contracts, in which a participant forfeits their own money if they do not reach a target weight, takes advantage of loss aversion, whereby a loss decreases our perceived wellbeing by more than similar sized gain increases wellbeing. Across these various interventions, there is consistent evidence that rewards help people to lose weight while they are being given rewards, but there is little evidence that rewards lead to sustained weight loss after rewards were removed. Except for two recent trials, patients who were given rewards regained weight, such that the weight loss at follow-up was not statistically different from usual care. Thus, the key question for incentivizing weight loss is not only how to get patients to lose weight, but also how to structure the rewards so that patients maintain the weight loss after rewards are removed.

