**Table 1. Three model studies of financial rewards for weight loss, and the proposed study**

Study characteristics	JAMA (2008) 	JGIM (2011) 	Annals (2013) 	Proposed study
Setting	Philadelphia VAMC (95% male)	Philadelphia VAMC (83% male)	Employees of Children's Hospital (89% female)	Seattle VAMC
Weight loss goal	1 lb./week	1 lb./week	1 lb./week	1 lb./week
Trial arms (participants per arm)	Usual care (n=19) Lottery: expected value ~\$90/month; (n=19) Deposit contract: max \$75/month (n=19)	Usual care (n=22) Deposit contract: max \$84/month (n=44)	Usual care (n=35) Individual: \$100/month (n=35) Group: \$500/month split among 5 patients (n=35)	Usual care (n=80) Financial lottery (n=100): expected value \$100/month; Non-financial raffle (n=100): expected value ~\$100/month.
Duration of rewards/total follow-up	16 weeks/28 weeks	32 weeks/68 weeks	24 weeks/36 weeks	16 weeks/32 weeks
Weight change at termination of rewards (lbs.)	Usual care: -2.9 Lottery: -13.1* Deposit contract: - 14.0*	Usual care: -1.2 Deposit contract: - 8.6*	Usual care: -1.1 Individual: -3.7 Group: -10.6*	Min detectable difference Usual care: -1.6 Lottery: -8.1 Raffle : -8.1
Weight change at follow-up (lbs.)	Usual care: -4.4 Lottery: -9.2 Deposit contract: - 6.2	Usual care: -0.3 Deposit contract: - 1.2	Usual care: -0.9 Individual: -1.8 Group: -7.5*	Min detectable difference Lottery: -3.1 Raffle : -8.1

Our target population for this study is overweight or obese Veterans, ages 18-69. Please see section 5.4 for additional information on our inclusion/exclusion criteria.

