The website has two data entry options: weight entry and survey (website mock up). The participants will enter in their weight on a predetermined week day as determined by them. We will encourage them to continue to do this for one year. They will be instructed to enter in the weight exactly as it is shown on the scale XXX.X. For the follow-up participant survey, it be available starting on the day it is due (16 weeks, 32 weeks and 1 year) and for three weeks after. At baseline, the participant can complete the survey anytime between baseline and two days hours before their first weight is due. The study coordinator will demonstrate accessing the website by logging in to a test account. The participant is weighed and the weight reading is entered in to the portal by the coordinator in the administrator website. This weight measurement is the baseline measurement for the study. Section 7 below covers privacy matters related to text messaging and/or email reminders and the portal.

The patient portal is a secure federal government website. All data is housed at the VA Austin Data Center. The website is designed and created by the VA Cooperative Studies Program Clinical Research Pharmacy Coordinating Center in Albuquerque with all information stored behind the VA firewall on VA servers in Austin, TX. None of the information entered in to the portal is associated or connected to the study participant. The participant will only be able to access the portal by using their login name and temporary password provided at enrollment. The first time the participant logs in they will be forced to change their password. Their name and any other identifier is never associated with the website. The crosswalk linking the participant's name and portal login information will always be kept in the secure J:drive folder. Only the study team will have access to it. Data entered into the website (weights and survey responses) and user ID will be exported from the portal (website) in a comma delimited file (.csv) by the study team in Seattle and saved directly onto the secure J:drive study folder.

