Hypothesis 1c implies a test of superiority and will be assessed using two-sided tests of  $(\beta_3 = \beta_2)$  in comparisons of weight change from week 16 to week 32 and 12 months, respectively. We will use weight change at week 16 in place of weight at baseline in equation 1, such that differences in weight regain between treatment arms will be adjusted for weight lost over weeks 1-16.

Because all secondary outcomes are continuous variables, a similar equation will be used to assess changes in secondary outcomes. These analyses explore how rewards affect constructs that are believed to mediate the effect of rewards on weight loss.

Missing weight measures will be imputed using data from patients' medical records for routine medical visits and methods developed and tested via simulation by [name] et al. These methods involve estimating longitudinal mixed-effects linear models of weight collected both through the trial and at routine clinic visits as a function of polynomials of time since enrollment, with random components for patient intercept and time, and using the predicted values from this model for any post intervention day as an estimate of what the patient's weight would have been on that day if he/she kept their follow-up appointment.

We assumed a standard deviation of 11.0 lbs. for weight loss based on the results of the JAMA (2008) and JGIM (2011) trials that were conducted in the VA and demonstrated statistically significant differences in

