## 5.7 Withdrawal of Subjects

Eligibility for rewards both financial and non-financial will be stated in the informed consent.

**5.7.a. Active withdraw.** Any participant may at any time notify the Principal Investigator or research coordinator(s) that they no longer wish to participate in the study and they will be considered withdrawn and will no longer participate in study procedures or activities. We will make every attempt to have a final study visit with the participant, ideally lining up with one of the three scheduled follow-up visits. For example, if a subject expresses that they'd like to withdraw from the study at week 11, we will halt all study procedures but will ask the participant if they could still come in for their week 16 visit and complete the interview. If they are not interested in coming in for a final study visit, and if they still have their Blipcare scale and/or Connect device, we will mail them a pre-paid box to return those items and they will be withdrawn immediately. If a final study visit is possible a final weight and survey will be recorded. At this point in time, depending on the arm of the study the participant was randomized to, they will be told the total amount they can expect to receive in the mail, or they will be notified of the non-financial reward(s) they have earned.

**5.7.b. Passive withdraw.** This study has multiple time-sensitive in person meetings, portal and phone communications. If we do not hear from a participant within 3 days of a missed in-person meeting we will call them and reschedule (Appendix O). If we do not reach them, we will make up to three total attempts to contact them. If the participant misses four weekly weight entries in a row we will make up to three attempts to contact them for every four week stretch they miss. We will make up to 30 total attempts to reach them via phone, voicemail, postcard and letter (Appendices E, O, Q and P), over the course of 19 weeks if we do not hear from them after the baseline appointment.

For each week the participant doesn't respond after the initial week a total of 3 attempts will be made to contact participants for each occurrence of not responding to study staff inquiries. Inquiries include reminder text messages, emails, phone calls from study staff and postcards.

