After the participant agrees to provide Carematix with their information (see Appendix A, informed consent), during the enrollment process, Blipcare scales will be assigned a study ID. The study team will have the crosswalk and will match participants to the weight data once the SSH transmission is complete. This is an added protection to protect against breach of confidentiality. No identifiable information will be transmitted to Blipcare or Carematix. Not all patients will receive the Connect devices because the cellular device and monthly contracts are costly. We will compare the self-reported weights with weights recorded on the Blipcare devices to see if there is any evidence that patients were misrepresenting their weights in order to earn an incentive. If patients do not receive a Connect device, we will download the stored data on the scale when they return them at their 16-week visit. Wirelessly transmitted weights from these scales will not be used as a substitute for self-reported weights. We will report the percentage of self-reported weights that were less than any wirelessly transmitted weights. We will also explore the extent to which weights collected at routine medical encounters could have been substituted for study-collected weights without loss of study integrity. We will estimate mixed effect linear models using weights collected at clinical encounters as a function of time, treatment arm, and treatment-by-time interactions. We will compare the difference in weight loss across treatment arms estimated from these models with the trial results. If the inferences are the same, then future weight loss studies could be conducted using primarily weight data from routine clinical encounters.

**9.1.e. Participant interviews.** All interviews will be recorded using Skype for Business, a VA-issued recorder, or the Audacity software program, and will be saved directly or immediately transferred onto the secure VA network, in an access-restricted folder behind the VA firewall. ATLAS.ti software will be used to code the interview findings. The ATLAS.ti software is located on the terminal server within the HSR&D COIN in Seattle.

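### Missing weights are filled by one prediction from a mixed model that does not list treatment arm, so the week-32 arm contrasts can be biased in either direction when later weights are sparse

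*Combined protocol and SAP*

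**What the plan says.** Section 5.6.a (Data Analysis) imputes missing weights from a longitudinal mixed model of trial weights and routine clinic weights. Weight is modelled "as a function of polynomials of time since enrollment, with random components for patient intercept and time". The fill is made by "using the predicted values from this model for any post intervention day as an estimate of what the" patient would have weighed at the missed visit. The section cites reference 23 for the method. It does not mention arm, multiple draws, a variance correction or a sensitivity analysis for missing weights.

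The completed data enter Equation (1), whose coefficients of interest are contrasts between arms. The primary outcome is week 32, which is 16 weeks after rewards stop (section 3.0). Hypothesis 1c uses "comparisons of weight change from week 16 to week 32 and 12 months, respectively".

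Arm terms are named elsewhere. Section 9.1.d plans "mixed effect linear models using weights collected at clinical encounters as a function of time, treatment arm, and treatment-by-time interactions", but only as an exploratory check on clinic weights. Section 5.6.a also offers a GEE with arm-by-period interactions, as an optional gain in efficiency.

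On which weights exist: participants enter weekly weights in the portal, and section 5.1.a says "We will encourage them to continue to do this for one year". Since March 2020, visit weights may be self-reported by phone. The withdrawal example in section 5.7.a, for a participant leaving at week 11, reads "we will halt all study procedures but will ask the participant if they could still come in for their week 16 visit".

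**The concern.** The trial asks what happens to weight after rewards stop, and expects arms to differ in exactly that. The model as listed has one mean curve for all arms and one linear slope per person. Two errors follow for a participant with few later weights.

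- With almost no post-baseline weights, the prediction falls back on the curve pooled over arms, and the arm contrast shrinks.
- With weights only up to about week 16, the personal slope carries the reward-period loss past the end of rewards. Regain is missed and sustained loss is overstated, mainly in an arm that regains.

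The primary contrast can therefore move in either direction, depending on when weights stop. That in turn depends on whether portal and phone-visit weights count as trial weights, which the plan does not say. A single prediction also treats imputed values as if they were observed.

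**Working it through.** **Inputs from the documents.** SD of change 11.0 lb, two-sided alpha 0.025, 20% loss to follow-up, 80/100/100 participants (section 5.6.a). Table 1 gives -8.1 lb in both reward arms at week 16 and "Lottery: -3.1 Raffle : -8.1" at follow-up. Usual care is -1.6 lb (Table 1 at week 16; section 5.6.a for prior control groups at the end of follow-up). True week-32 contrasts on this path are 8.1 - 1.6 = 6.5 lb (non-financial) and 3.1 - 1.6 = 1.5 lb (financial).

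**Assumptions, not in the documents.** Cubic time, 0 to 2 clinic weights a year, measurement noise of 2 to 3 lb, and dropout equal across arms and unrelated to outcome.

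**The plan's own figures.** Minimum detectable difference = (2.241 + 0.842) × 11 × sqrt(1/n1 + 1/n2). For 80 v 100 this is 3.083 × 11 × 0.150 = 5.09 lb (stated 5.1). For 80 v 200 it is 4.49 (stated 4.5), and for 100 v 100 it is 4.80 (stated 4.8). The plan states no figure for imputation bias.

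**Hand calculation at 20% missing.**

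- Baseline weights only: imputed participants carry no arm difference, so the estimate is 0.8 × 6.5 = 5.2 lb, short by 1.3 lb.
- Weights to week 16, slope fully carried forward: the week-16 difference of 6.5 lb doubles to 13.0 lb at week 32. For the financial arm the excess is 13.0 - 1.5 = 11.5 lb per imputed participant, and 0.2 × 11.5 = 2.3 lb overall. If both reward arms fully regain (true contrast 0), it is 0.2 × 13.0 = 2.6 lb. A single week-16 visit gives a less certain slope, hence more shrinkage and a smaller error.

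**Simulation of the method as listed, then Equation (1), at week 32.** Ranges span separately coded simulations.

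| Weights seen for the missing 20% | Contrast with usual care | True (lb) | Error (lb) |
|---|---|---|---|
| Baseline only | Non-financial | 6.5 | understated 1.2 to 1.4 |
| Baseline, about 2 clinic weights a year | Non-financial | 6.5 | understated 0.4 |
| Last weight at week-16 visit | Financial | 1.5 | overstated 0.7 |
| Weekly to week 16, then none | Financial | 1.5 | overstated 1.4 to 2.4 |
| Weekly to week 16, about 2 clinic weights a year | Financial | 1.5 | overstated 0.9 |
| Full regain, last weight at week-16 visit | Either reward arm | 0 | false loss 0.9 to 1.0 |
| Full regain, weekly to week 16, then none | Either reward arm | 0 | false loss 2.0 to 2.6 |
| Full regain, weekly to week 16, about 2 clinic weights a year | Either reward arm | 0 | false loss 1.2 |

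The error scales with the share missing: the first row becomes 0.6 lb at 10% and 2.0 lb at 30%.

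**Type I error.** Under full regain, with 280 participants, about one clinic weight a year and 1,000 simulated trials, one contrast at nominal 2.5% rejected in 3.5% (early dropout), 4.8% (last visit at week 16) and 10.7% (weekly weights to week 16). Full data gave 2.9%, 2.8% and 1.9%. The Monte Carlo standard error at 2.5% is sqrt(0.025 × 0.975 / 1000) = 0.5 points, so the first figure is not clearly raised. If rewards have no effect at any time and weights stop at week 16, either-arm rejection was 0.047 against 0.053 with full data: no inflation.

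**Hypothesis 1c (one simulation, not checked with separate code).** The true week-32 regain contrast on the Table 1 path is 8.1 - 3.1 = 5.0 lb. The estimate was 0.80 to 0.94 of the full-data value in all 15 dropout patterns with missed week-32 visits. At 12 months it was 0.79 to 0.98 under constant weekly regain. On the Table 1 path it was 0.79 to 0.95 in 12 of 16 patterns and 0.99 to 1.06 in the other 4.

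**What a repair does.** Adding arm and arm-by-time terms cut week-32 errors from between 1.3 lb understated and 2.1 lb overstated to between 0.1 lb understated and 0.45 lb overstated. Keeping a single prediction with arm in the model still failed: the contrast had SD 1.68 against a mean reported SE of 1.44, and rejected 5.5% at nominal 2.5%.

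**The case against.** **The text may be a summary of reference 23.** This stands in part. That paper may include arm terms or a variance correction. What the documents support is that the plan states none of these. It does list the model terms and the fill, and it names arm when it means to use it (section 9.1.d), so the listed method is the one to judge.

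**The larger errors need an unfavourable pattern.** This stands. They need all of the missing 20% to stop giving weights of any kind at week 16. The method uses routine clinic weights, the plan provides for repeated contact attempts and phone visits, and the section 5.7.a example does not say that clinic weights end.

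**The optional GEE has arm-by-period terms.** True, but it does not repair values already imputed without arm.

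**Stronger readings that the documents do not support.**

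- A reader might infer that full regain is the documented expectation. Section 2.0 says, with two exceptions, that "patients who were given rewards regained weight, such that the weight loss at follow-up was not statistically different from usual care". Non-significance is not a zero effect, and the statement covers financial rewards only. Every reward arm in Table 1 stays below usual care at follow-up (-9.2 and -6.2 v -4.4; -1.2 v -0.3; -1.8 and -7.5 v -0.9), and the plan's own raffle path holds at -8.1.
- A reader might infer a known inflation for the hypothesis 1b non-inferiority test. No figure is given here because the nominal level is unclear: section 5.6.a sets alpha at two-sided 0.025, yet its power of 0.94 reproduces at one-sided 0.025 (0.943) and not at 0.0125 (0.903).

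**Conclusion.** The concern holds for the method as written. At 20% missing, the week-32 bias runs from about 1.2 to 1.4 lb understatement of a 6.5 lb effect to about 0.7 lb overstatement of a 1.5 lb effect, or 1.4 to 2.4 lb if weekly weights enter the model and stop at week 16. These compare with a detectable difference of 5.1 lb. If reward arms lose weight and then fully regain it, the method can show a sustained loss of about 1 to 2.6 lb and inflate type I error. That is a null worth protecting against, not one that the documents report. Hypothesis 1c tends to shrink, which mainly costs power.

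The sizes rest on assumed variances, visit density and dropout patterns; the directions follow from the structure of the model. Bias is small when clinic or weekly weights continue near the visit, and type I error is not inflated by this route if rewards never work. The point should be fixed before analysis, with medium confidence in its size.

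**What to change.** In section 5.6.a:

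1. Add arm and arm-by-time terms to the mixed model, with time flexible enough for arm means to change direction after week 16. Knots and random effects are for the trial statistician to choose.
2. Either estimate the week-16, week-32 and 12-month contrasts directly from that model, or draw multiple imputations and combine them by Rubin's rules. Do not add arm while keeping a single prediction.
3. State whether portal and phone-visit weights enter the model. If reference 23 already includes arm terms or a variance correction, say so.
4. Report by arm how many imputed participants had no post-baseline weight, and how many had none after week 16.

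The cost is wording and modest programming, with no new data. Standard errors may be slightly larger: in one simulation of multiple imputation, about 1.6 to 1.8 lb for hypothesis 1a, against 1.4 to 1.8 lb as written. In three full-regain patterns that version gave an either-arm false-claim rate of 0.060, against 0.056 with full data. Its random effects resembled those used to generate the data, so the check should be repeated with the trial's own blinded variances.

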**Project Methods:** We will conduct a three-armed randomized trial of patient rewards for losing one pound per week over 16 weeks. The three treatment groups will receive financial rewards, non-financial rewards, or no rewards. We hypothesize that: 1) patients who receive non-financial rewards for weight loss over 16 weeks will have greater weight loss at 32 weeks than patients who do not receive rewards; 2) patients who receive non-financial rewards for weight loss over 16 weeks will experience weight loss at 16 weeks that is not inferior to the weight loss of patients who receive financial rewards; and 3) weight regain will be greater among patients who received financial rewards compared to patients who received non-financial rewards or no rewards. We will also conduct post-intervention qualitative interviews and perform a cost analysis.

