### 3.0 Objectives

The proposed study is based on the hypothesis that the regain found in prior reward studies was due in part to their use of financial rewards, and financial rewards may make patients especially susceptible to regain. Experiments in behavioral economics have found that when participants were provided financial rewards for performing a task, their behavior toward the task was defined by reciprocity—the effort the participants gave was proportional to the amount of money that they were given. When participants were given non-financial rewards, they exhibited no reciprocity—the effort was consistently high and did not vary with the quantity of the non-financial reward. These findings have been confirmed in field studies, and experiments using functional MRIs: money as a reward makes us think and behave differently. By using financial rewards, prior trials may have invoked money-market norms of reciprocity, such that patients' efforts toward weight loss were high when rewards were offered, and reduced when they were discontinued. We hypothesize that non-financial rewards, such as tickets to a Seattle Mariners baseball game, will not invoke reciprocity or the consequent weight regain. We also hypothesize that the affective or emotional characteristics of non-financial rewards can make them more powerful than financial rewards. A patient's thoughts about receiving a non-financial reward, such as tickets to baseball game, can create a positive emotional reaction that can be more salient than the cash value of the reward.

The goal of this study is to test, through a randomized trial, the effectiveness of providing obese Veterans with financial or non-financial rewards for losing 1 lb. per week over 16 weeks. The primary outcome is weight loss at 32 weeks—16 weeks after the discontinuation of the rewards. Secondary outcomes include weight loss at 16 weeks and 12 months. The specific aims are outlined below.

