#### **Aim 1. Conduct a 3-armed randomized trial of patient rewards for losing 1 lb. per week over 16 weeks.**

The 3 treatment groups will receive financial rewards, non-financial rewards, and no reward (usual care).

- Hypothesis 1a: Patients who receive non-financial or financial rewards for weight loss over 16 weeks will have greater weight loss at 32 weeks than Veterans who do not receive rewards.

- Hypothesis 1b: Patients who receive non-financial rewards for weight loss over 16 weeks will experience weight loss at 16 weeks that is not inferior to the weight loss of Veterans who receive financial rewards.
- Hypothesis 1c: Weight regain between week 16 and the 32-week and 12-month follow-up, respectively, will be greater among Veterans who received financial rewards compared to Veterans who received non-financial rewards or no rewards.

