### 5.6.a. Data Analysis

All data will be analyzed at VA Puget Sound Health Care System by one of the data analysts and/or investigators.

We will use an intent to treat analysis. To test each hypothesis we will estimate an equation of the form

$\Delta Y_{it} = \beta_0 + \beta_1 Weight_{i0} + \beta_2 M_i + \beta_3 F_i + u_i$  (1) where  $\Delta Y_i$  is change in weight from baseline to follow-up time t

for patient i;  $Weight_{i0}$  is baseline weight for patient i; F is the financial rewards (arm 2); M is an indicator for assignment to non-financial rewards (arm 3); and u is a random error. To gain a small amount of efficiency we can also estimate (1) using repeated measures of change in weight from baseline to the three follow-up measures (16 weeks, 32 weeks and 12 months) using GEE models of the same form as equation (1), except with dummy variables for follow-up periods and interactions between these variables and the treatment group dummies.

Hypothesis 1a implies a test of superiority and will be assessed using two-sided tests of  $\beta_2 = 0$  for non-financial rewards, and  $\beta_3 = 0$  for financial rewards. Large positive or negative values of  $\beta_2$  and  $\beta_3$  are evidence against the null hypothesis of no difference between reward and non-reward groups.

Hypothesis 1b implies a non-inferiority test. We will reject the hypothesis that non-financial rewards are inferior to financial rewards if  $\beta_2$  is statistically significantly greater than zero (i.e., there was statistically significantly more weight loss in the non-financial reward arm than in usual care) and if  $(\beta_3 - \beta_2) < 2.5 kg$ , where  $(\beta_3 - \beta_2)$  is the adjusted difference in mean weight loss between the financial and non-financial reward arms, and 2.5 kg is half the 5 kg weight loss assumed to be clinically significant. Although there are no defined rules for choosing a range of indifference for a non-inferiority test, researchers often use half the minimum clinically significant amount. Values of  $(\beta_3 - \beta_2)$  that are statistically significantly larger than 2.5 kg are evidence against the hypothesis that non-financial rewards are not inferior to financial rewards.

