weight loss at the end of the reward period. We used a two-sided alpha of 0.025 to account for the multiple comparisons between treatment groups (including for hypotheses 1b and 1c, which compare only two groups). We chose a clinically meaningful minimal detectable difference of 11 lbs. (5 kg). This was the weight loss experienced by the lifestyle management arm of the Diabetes Prevention Program randomized trial, which experienced lower rates of the incidence of diabetes. According to data from the 2012 NHANES, 11 lbs. is 5% of the average weight of 233 lbs. for obese men, and the FDA defines a weight loss drug as clinically effective if mean weight loss in the drug group is at least 5% of baseline weight. With these assumptions we would require full data on 21 patients per treatment arm at follow-up, or 28 assuming 20% loss to follow-up, in order to have 80% power to reject hypothesis 1a. In order to conduct subgroup analyses with reasonable precision, and to increase the power to detect differences in weight regain between reward groups (hypothesis 1c), we will increase enrollment to 80 patients in the no-reward arm, and we will increase the ratio of patients randomized to control versus either reward group from 1:1 to 1:1.25 for a total of 280 patients (80 usual care+100 in each reward arm). This provides a minimum detectable difference of 5.1 lbs. between treatment arms, and 4.5 lbs. if the reward arms are combined. In the three studies in Table 1, the average weight loss in the control groups at the end of follow-up was 1.6 lbs. Thus, we expect 80% power to detect weight loss as small as 6.7 lbs. in each reward group. At the end of the reward period, the average weight losses in the reward groups was 10 lbs. (range, 14 to 3.7) among the trials in Table 1. In the JAMA (2008) study, 50% of the reward group achieved their goal of 16 lbs. weight loss in 16 weeks. Thus, we have the power to detect achievable and clinically important weight losses across treatment arms.

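### Hypothesis 1a: testing the two week-32 comparisons with Holm's step-down would be a cheap, modest gain over the valid 0.025 split used for planning

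*Combined protocol and SAP*

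**What the plan says.** Section 3.0 sets the primary endpoint: "The primary outcome is weight loss at 32 weeks". Hypothesis 1a under Aim 1 covers both reward arms: "Patients who receive non-financial or financial rewards for weight loss over 16 weeks will have greater weight loss at 32 weeks" than those without rewards. Section 5.6.a turns this into two separate tests: "Hypothesis 1a implies a test of superiority and will be assessed using two-sided tests of" β2 = 0 (non-financial) and β3 = 0 (financial). Both compare with the same usual-care arm.

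The paragraphs of section 5.6.a that describe the tests give no significance level. The level appears only in the later power paragraph: "We used a two-sided alpha of 0.025 to account for the multiple comparisons between treatment groups", with the addition "including for hypotheses 1b and 1c, which compare only two groups". No step-down, Dunnett, hierarchical or gatekeeping procedure is described anywhere. The power statement is made arm by arm: "we expect 80% power to detect weight loss as small as 6.7 lbs. in each reward group".

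The Abstract (Project Methods) words the week-32 superiority hypothesis for one reward arm only: "patients who receive non-financial rewards for weight loss over 16 weeks will have greater weight loss at 32 weeks" than patients without rewards.

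**The concern.** A level of 0.025 for each of two comparisons is 0.05/2, a Bonferroni split. If it is also the decision rule, it leaves some power unused. Once one of the two null hypotheses has been rejected, only one is left that could be rejected falsely, and it can be tested at the full 0.05 without taking the family-wise error above 5%. Holm's procedure does exactly this.

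The gain falls on the second comparison, and hypothesis 1a as worded in Aim 1 expects both rewards to beat no reward. Suppose one arm is clearly positive and the other has p = 0.03. Under a fixed 0.025 the second arm is not significant; under Holm it is. Because the plan gives a level for planning but no decision procedure for the analysis, that case could be argued either way once the result is known.

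**Working it through.** **Inputs.** From section 5.6.a: "We assumed a standard deviation of 11.0 lbs. for weight loss"; arms of 80 (usual care), 100 and 100; two-sided 0.025; 80% power; clinically meaningful difference 11 lb; 20% loss to follow-up; usual-care loss 1.6 lb. From Table 1, follow-up row: lottery 3.1 lb and raffle 8.1 lb lost.

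**Step 1: the plan's figure.** The standard error of one reward-minus-control difference is 11 × √(1/80 + 1/100) = 11 × 0.15 = 1.65 lb. The detectable difference is (2.241 + 0.842) × 1.65 = 5.09 lb, against 5.1 stated. With alpha 0.05 it would be (1.960 + 0.842) × 1.65 = 4.62 lb. So 0.025 was used, and 5.1 is right for it. The same formula gives 4.49 lb for 80 versus 200 (stated 4.5) and 4.80 lb for 100 versus 100 (stated 4.8).

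**Step 2: dependence of the two tests.** The shared control arm gives a correlation of (1/80)/(1/80 + 1/100) = 0.0125/0.0225 = 0.556.

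**Step 3: the two rules.** With Z1 and Z2 bivariate normal:
- Fixed split: reject arm i if |Zi| > 2.241.
- Holm: reject arm i if |Zi| > 2.241, or if |Zi| > 1.960 and the other |Zj| > 2.241.

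Holm needs one |Z| above 2.241 before it rejects anything, so the probability of at least one rejection is the same under both rules. The probability of rejecting both is the sum of the two per-arm powers minus that probability.

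**Step 4: 5.1 lb in both arms, complete data.** The mean of each Z is 5.1/1.65 = 3.09. Per-arm power is 0.8022 (fixed) and 0.8463 (Holm). At least one: 0.9077. Both: 2 × 0.8022 − 0.9077 = 0.697 (fixed) and 2 × 0.8463 − 0.9077 = 0.785 (Holm). A simulation of 2 million draws agreed to within 0.001.

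**Step 5: other scenarios.** The 64/80/80 row removes 20% of each arm, with no imputation.

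| True difference (lb) | Arm sizes | Per arm, fixed | Per arm, Holm | Both, fixed | Both, Holm | At least one |
|---|---|---|---|---|---|---|
| 5.1 and 5.1 | 80/100/100 | 0.802 | 0.846 | 0.697 | 0.785 | 0.908 |
| 5.1 and 5.1 | 64/80/80 | 0.700 | 0.751 | 0.565 | 0.668 | 0.834 |
| Raffle 6.5, lottery 1.5 | 80/100/100 | 0.955; 0.092 | 0.955; 0.148 | 0.092 | 0.148 | 0.956 |
| 11 and 11 | 80/100/100 | 1.00 | 1.00 | 1.00 | 1.00 | 1.00 |

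The third row uses Table 1's follow-up values less the usual-care loss: 8.1 − 1.6 = 6.5 and 3.1 − 1.6 = 1.5.

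**Step 6: error rates.** With no effect in either arm, the chance of any false rejection is 0.046 under both rules. If one reward does nothing and the other has a true difference of 5.1 lb, the error on the ineffective arm is 0.025 (fixed) and 0.042 (Holm). If the other has 11 lb, it is 0.025 and 0.050.

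**The case against.** The strongest reply is that nothing here is broken. A 0.05/2 split is valid, and the plan's detectable differences are correct for it. That stands.

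A reader might infer that the stated 80% is wrong because the chance of showing both arms is only 70%. The documents do not support this: the 80% is claimed for each arm, joint power is never claimed, and Holm does not change the chance of at least one positive arm.

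A reader might also infer that the plan commits itself to calling p = 0.03 negative. That goes beyond the text, since 0.025 is given as a planning assumption and no decision procedure is written down.

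Nor is Holm free. The error on an ineffective second arm can double to 0.05, which is within the limit for hypothesis 1a but is a real trade. The 5% also covers only the two 1a tests. Counting 1b, and 1c at two times, the plan has five tests at 0.025, with nominal levels that sum to 5 × 0.025 = 0.125. Holm within 1a does nothing about that sum, and letting one test use 0.05 loosens it slightly.

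The favourable scenario can fairly be questioned too. An equal 5.1 lb effect is the detectable difference, not a forecast, and the study's thesis is that the reward arms diverge after rewards stop. Table 1's values show how little is then gained. The 20%-loss row ignores the planned imputation from medical-record weights.

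Finally, if the Abstract's single-arm hypothesis is the primary one, no split is needed and the point falls away. What survives is that, with both arms in the family, Holm rejects whenever the split does and needs no more patients.

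**Conclusion.** The point holds as an efficiency improvement, not as an error in the plan. With both reward arms in the week-32 family and a true difference of 5.1 lb in each, Holm adds about 4 percentage points of power per arm (0.80 to 0.85 after rounding) and 9 for showing both (0.70 to 0.785). With 20% loss and no imputation the gains are about 5 points (0.70 to 0.75) and 10 points (0.565 to 0.67). The gain shrinks to the weaker arm alone when effects diverge as in Table 1, and to nothing at 11 lb.

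These figures rest on the plan's SD of 11 lb, a normal approximation, the planned 280 patients, and no allowance for the baseline-weight adjustment. The 5% guarantee applies to hypothesis 1a only, but it holds under any dependence between the two tests.

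**What to change.** First reconcile the Abstract with Aim 1 and state whether one or both reward arms are in the primary week-32 family. If both are, add to section 5.6.a that β2 and β3 at week 32 will be tested by Holm's step-down at an overall two-sided 0.05: the smaller p-value at 0.025 and, only if that is significant, the other at 0.05. Keep 0.025 as the planning level and for hypotheses 1b and 1c, and report 97.5% confidence intervals.

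The cost is one sentence, fixed before outcomes are compared by arm, and no patients. The text should acknowledge two consequences: error on an ineffective arm may reach 0.05 when the other reward works well, and a 97.5% interval may include zero for an arm that Holm declares significant at the second step.
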